10.4.3.1 Primary Efficacy Endpoints

The primary efficacy endpoint is percent change from baseline to Day 150 in LDL-C.

The primary analysis will be conducted using ANCOVA model based on the multiply imputed datasets (100 total). The ANCOVA model will include the fixed effect of treatment group (Inclisiran or placebo) and baseline LDL-C as a covariate. Treatment effects from these 100 ANCOVA analyses will then be combined using Rubin's method. The difference between treatment groups in mean change from baseline to Day 150 in LDL-C and corresponding two-sided 95% confidence interval will be provided. The p-value for testing equal mean change from baseline to Day 150 in LDL-C will also be provided.

The missing data imputation for primary analysis will be the Washout-model-based approach. The washout model can be thought of as a modified control-based Pattern-Mixture Model (PMM) that

will be used to explore the possibility of data missing not at random (MNAR) for subjects who discontinued the study early.

Sensitivity analysis for the primary efficacy endpoint will use Wilcoxon rank-sum test, a nonparametric analysis method, as well as the two-sample t-test.

Also, we will perform sensitivity analyses to explore the dropout pattern and its possible impact on treatment comparisons in order to support the robustness of the conclusion drawn from the primary analysis using data up to Day 180. Pattern-Mixture Model (PMM) will be used to check the robustness when data missing not at random (MNAR) for subjects who discontinued study treatment. A control-based pattern-mixture model will be utilized. Multiple imputation will be used to account for uncertainty in the imputation process and results from a Mixed-effects Model for Repeated Measures (MMRM) on the imputed datasets will be combined using Rubin's method. Furthermore, a tipping point analysis will be performed to search for the tipping point that reverses the study conclusion. In addition, an analysis based on a Mixed-effects Model for Repeated Measures (MMRM) without multiple imputation will be performed.

The primary analysis and sensitivity analyses will be performed on both ITT and mITT populations. Details of the sensitivity analysis specified above will be in the SAP.

10.4.3.2 Secondary Efficacy Endpoints

For the first four key secondary endpoints, the following efficacy analyses will be performed on the ITT and mITT populations:

- Similar to the primary analysis of the primary efficacy endpoint, the ANCOVA model will be used on the multiply imputed datasets (100 total) – Washout based approach. Treatment effects from these 100 ANCOVA analyses will then be combined using Rubin's method.
- MMRM model will be used on the multiply imputed datasets (100 total) – PPM based imputation. Treatment effects from these 100 ANCOVA analyses will then be combined using Rubin's method
- Analysis based on a Mixed-effects Model for Repeated Measures (MMRM) without multiple imputation will be performed.

For the key secondary endpoint of $\geq 30\%$ LDL-C reduction from baseline to Day 150, a logistic regression model with treatment as the effect will be used, and the odds ratio and its 95% confidence interval will be provided. The multiply imputed datasets created from both the washout model and the control-based PMM will be utilized in this analysis.

For the other secondary endpoints specified in [Section 3.4](#), generally descriptive and graphical summaries by treatment group will be presented for the ITT population. The two-sided 95% confidence interval may be provided for continuous variables based on the MMRM model. Odds ratio and 95% confidence interval may be provided for binary variables. Nominal p-values may be provided when applicable. Details of the analyses for the secondary endpoints are specified in the SAP.

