Unless specified otherwise, the ITT will be the primary analysis population for efficacy analysis and Safety population will be the primary population for safety analysis in this study. mITT population will be used to confirm the efficacy.

Statistical Analysis:

Statistical comparisons will only be performed for the Part 1 of the study. The statistical analysis for study Part 2 is descriptive.

Summary statistics for continuous variables will include the number of subjects, mean, median, standard deviation or standard error, minimum and maximum. For categorical variables, the frequency and percentage will be given.

The primary endpoint is the percent change from baseline in LDL-C following 150 days of treatment.

The primary analysis will be conducted using ANCOVA model based on the multiply imputed datasets (100 total) - Washout based approach. The ANCOVA model will include the fixed effect of treatment group (Inclisiran or placebo) and baseline LDL-C as a covariate. Treatment effects from these 100 ANCOVA analyses will then be combined using Rubin's method. The difference between treatment groups in mean change from baseline to Day 150 in LDL-C and corresponding two-sided 95% confidence interval will be provided. The p value for testing equal mean change from baseline to Day 150 in LDL-C will also be provided. For the key secondary endpoints, the efficacy analyses will be similar to the primary analysis of the primary efficacy endpoint, the ANCOVA model will be used on the multiply imputed datasets (100 total) - Washout based approach. Treatment effects from these 100 ANCOVA analyses will then be combined using Rubin's method.

Additionally sensitivity analysis including MMRM on imputed data using PMM and without imputation will be performed for both primary and key secondary endpoints except for the endpoint of $\geq 30\%$ LDL-C reduction from baseline to Day 150, which will be analyzed using the logistic regression model with treatment as the effect.

This study is sufficiently powered for the hypothesis testing in the primary and key secondary endpoints, all other endpoints are supportive hence no adjustment for multiplicity is planned.

Safety summaries will include the incidence of AEs, summaries of laboratory parameters, vital signs, and ECGs.

Table of contents

Protocol Synopsis	2
Table of contents.....	8
List of tables.....	12
List of figures.....	12
List of abbreviations	13
Amendment 1 (08-Oct-2020).....	16
1 Introduction.....	26

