1.2.2.2.3 Study ORION-2 (MDCO-PCS-16-02, CKJX839A12202)

ORION-2 (MDCO-PCS-16-02, CKJX839A12202; completed) was a Phase II, open label, single arm, multicenter pilot study in subjects with homozygous familial hypercholesterolemia. Four subjects were randomized and received open-label inclsiran sodium 300 mg SC on Day 1. The subsequent dosing interval was determined by PCSK9 level at Day 60 or 90 or rate of change of PCSK9 between Days 60 and 90. Three subjects received a second injection because mean serum PCSK9 levels were not suppressed by $> 70\%$ at Day 60 or 90, as compared to baseline.

Inclisiran treatment resulted in robust and durable reductions in PCSK9 levels in all four subjects treated at a dose of 300 mg SC. Three of the four subjects also had significantly reduced levels of LDL-C. One subject had a significant reduction in PCSK9 but not a concomitant reduction in LDL-C. The mean percentage LDL-C reduction from baseline was 12.3% and 21.0% at Day 90 and Day 180, respectively. The maximum reductions in LDL-C were at Day 120 for two subjects and at Day 150 for a third subject. Therefore, the second dose achieved a greater reduction in LDL-C than after the first dose.

The mean percentage PCSK9 reduction from baseline was 59.0% and 62.9% at Day 90 and Day 180, respectively. Decreases in other lipids, lipoproteins, and apolipoproteins were commensurate with the decreases in LDL-C.

No safety observations were noted and inclisiran was generally well tolerated. Three of the four subjects reported adverse events. There were no deaths and one SAE (unstable angina, which was not considered related to study drug). No subjects withdrew due to an adverse event and no adverse events at the injection site were reported.

A number of notable elevations chemistry parameters were observed. One subject with an elevated total bilirubin ($>1x$ ULN) at screening experienced a single elevation of total bilirubin $>2x$ ULN on Day 120. There were no ALT or AST elevations $>3 \times$ ULN or CK elevations $>5x$ ULN. None of the subjects developed anti-drug antibodies.

The results from this pilot study support the 300mg dose and dose regimen for the ongoing Phase III ORION-5 study in HoFH.

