10.1 Sample Size

The sample size calculation was performed with the hypothesis that the difference of mean percent change from baseline to Day 150 between inclisiran and placebo will be >20% (20% standard deviation) in subjects with HoFH when treated with inclisiran. The sample size of at least 45 subjects (randomized 2:1 to inclisiran : placebo), with at least 30 subjects in the inclisiran arm, will provide >80% power to detect a 20% reduction of LDL-C levels from baseline in the inclisiran group compared to that in the placebo at one-sided significance level of 0.025 based on two-sample t-test.

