10.4.3 Efficacy Analysis

This study is sufficiently powered to show the effect in the primary and key secondary endpoints, all other secondary [REDACTED] endpoints are supportive hence statistical testing on all other secondary [REDACTED] endpoints will be performed only if the null hypothesis on primary and the key secondary endpoints are rejected. No adjustment for multiplicity is planned among the other secondary [REDACTED] endpoints.

The ITT population will be the primary population for the efficacy analysis. Efficacy analysis may also be performed for the mITT population as supportive analysis.

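### The protocol's claim of sufficient power for the key secondary endpoints does not hold for the ≥30% LDL-C responder endpoint at the design difference of 20 points: power is about 39% to 63%, not 80%

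*Protocol*

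**What the plan says.** Section 10.1 sizes the trial on the mean percent change in LDL-C from baseline to Day 150. It assumes a difference above 20%, an SD of 20%, at least 45 subjects at 2:1 and a two-sample t-test at one-sided 0.025, and concludes that this "will provide >80% power to detect a 20% reduction of LDL-C levels from baseline in the inclisiran group compared to that in the placebo". No other endpoint has a calculation.

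Section 3.4 lists five key secondary endpoints. Four are continuous; the fifth is the proportion with an LDL-C reduction of at least 30% at Day 150. Section 10.4.3 then states: "This study is sufficiently powered to show the effect in the primary and key secondary endpoints". The synopsis agrees: "This study is sufficiently powered for the hypothesis testing in the primary and key secondary endpoints".

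For the responder endpoint, Section 10.4.3.2 says that "a logistic regression model with treatment as the effect will be used, and the odds ratio and its 95% confidence interval will be provided", and adds: "The multiply imputed datasets created from both the washout model and the control-based PMM will be utilized in this analysis". It names no estimator, test statistic or pooling rule for this endpoint, and it closes with: "Details of the analyses for the secondary endpoints are specified in the SAP".

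**The concern.** Power for a difference in means does not carry over to a dichotomy of the same variable. The cut-off of 30% lies beyond the 20-point design effect. If the placebo mean is near zero, fewer than half of the inclisiran subjects would be expected to cross it, and the placebo arm has only 15 to 19 subjects. The power statement nevertheless covers this endpoint without qualification.

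If the statement is wrong, a non-significant responder result would be read as evidence against an effect from an adequately powered comparison. Section 10.4.3 also makes testing of the other secondary endpoints conditional on rejecting the key secondary null hypotheses. That consequence is limited, because Section 10.4.3.2 treats those other endpoints as generally descriptive.

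**Working it through.** **Inputs.** Difference 20 points, SD 20, arms of 30 and 15, one-sided 0.025, equivalent to two-sided 0.05 (Section 10.1). 56 subjects enrolled (Amendment 1 rationale); the split of 37 and 19 is assumed from 2:1. The protocol gives no placebo mean, so 0 is assumed and varied. Percent changes are assumed normal, with no missing data.

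**1. The protocol's own figure.** SE = 20 × √(1/30 + 1/15) = 6.32; noncentrality = 20/6.32 = 3.16; 43 degrees of freedom. Power is 87.1%, so the claim of more than 80% is correct for the primary endpoint. At 37:19, SE = 5.64, noncentrality = 3.54 and power is 93.6%.

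**2. Responder rates from the same inputs.** Rate = Φ((−30 − mean)/20).
- Placebo, mean 0: Φ(−1.5) = 6.7%.
- Inclisiran, mean −20: Φ(−0.5) = 30.9%.

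**3. Responder power.** The product of the two binomial probabilities is summed over all 2×2 tables in which the test rejects in favour of inclisiran at two-sided 0.05. The difference is held at 20 points and the SD at 20. The last column gives the difference needed for 80%, from the lowest to the highest over the three tests and both sample sizes.

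| Placebo mean | Rates, placebo vs inclisiran | Power % at 30:15 (Fisher / chi-square / LR) | Power % at 37:19 (Fisher / chi-square / LR) | Points for 80% |
|---|---|---|---|---|
| +5 | 4.0% vs 22.7% | 21.9 / 33.2 / 49.8 | 36.1 / 43.3 / 55.9 | 25.5 to 30.3 |
| 0 | 6.7% vs 30.9% | 39.2 / 49.8 / 53.9 | 51.1 / 57.5 / 63.0 | 23.7 to 28.0 |
| −5 | 10.6% vs 40.1% | 50.3 / 59.1 / 60.5 | 59.0 / 69.1 / 70.1 | 22.2 to 26.5 |
| −10 | 15.9% vs 50.0% | 55.5 / 63.5 / 66.8 | 68.3 / 76.1 / 76.2 | 20.9 to 25.6 |

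No cell reaches 80%. With 6.7% vs 30.9% at 2:1, the normal-approximation formula needs about 96 subjects in total for 80% power.

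**4. Where the claim would hold.** At placebo mean 0 and SD 20, a 25-point difference gives 67% (Fisher) to 76% (LR) at 30:15 and 77% to 85% at 37:19. A 30-point difference gives 87% to 92% and 93% to 96%. At exactly 20 points, SD 15 with placebo mean −10 gives Fisher 79% and 88%, and LR 86% and 93%.

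**5. Sparse cell.** The expected number of placebo responders at mean 0, SD 20 is 15 × 0.0668 = 1.0, or 19 × 0.0668 = 1.3. The chance of none is 0.9332^15 = 35%, or 0.9332^19 = 27%. Changing one assumption at a time gives about 4% (mean −10, n = 19) to 71% (SD 15, n = 15). A maximum-likelihood fit to 9/30 vs 0/15 returned a log odds ratio of about 22 with a standard error of about 12,444, so there is no usable estimate or upper limit. Imputation fills only missing values and does not remove the problem.

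**The case against.** The strongest reply on power is that Section 10.1 hypothesises a difference above 20%, so a true effect of 25 points or more fits the design and the claim could then be true. That stands, and a reader who infers that power is inadequate at every plausible effect goes too far. But Section 10.1 states its power for detecting a 20% reduction, and an unqualified power claim should hold at that value. The only HoFH data in the protocol come from four subjects in a single-arm pilot: "The mean percentage LDL-C reduction from baseline was 12.3% and 21.0% at Day 90 and Day 180, respectively". They are too few to settle the matter, and they give no ground for assuming a much larger effect.

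A second reply is that the shortfall depends on an assumed placebo mean and on normality. It does, but at the protocol's SD no placebo mean from −10 to +5 brings any of the three tests to 80%. The smaller SD that would do so is not the protocol's.

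A reader might also infer that Section 10.4.3.2 commits the trial to an analysis that breaks down when no placebo subject responds. The protocol does not support that. It does not specify ordinary maximum likelihood, Wald inference or Rubin pooling for this endpoint. A penalised or exact fit would satisfy its wording, and the details are left to an SAP that is not shown. Even with an infinite odds ratio, a likelihood-ratio test and a finite lower profile limit remain available.

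Finally, enrolment is complete and Part 1 is unblinded, so a correction changes no conduct. That limits the point's weight but does not make the sentence true.

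**Conclusion.** The power statement in Section 10.4.3 and the synopsis is wrong as written for the responder endpoint. At the design difference of 20 points and SD 20, with normality and placebo mean 0, power is 39% to 54% at 30:15 and 51% to 63% at 37:19. Over placebo means from −10 to +5 it is about 22% to 76%. With SD 20 and placebo means from 0 to −10, 80% needs a difference of roughly 21 to 28 points, depending on the test, arm sizes and placebo mean. A smaller SD such as 15 with a negative placebo mean can reach it at 20 points.

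The primary endpoint's stated power is correct. The four continuous key secondary endpoints have no calculation of their own either, but nothing here shows that they lack power. The possible empty placebo cell is a secondary note: plausible enough to plan for, with a probability that rests on assumed placebo behaviour, and not an error in the protocol.

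**What to change.** In Section 10.4.3 and the synopsis, do one of two things:
- limit the power sentence to the endpoint that the Section 10.1 calculation covers; or
- add the responder power and its assumptions. For example: at a 20-point difference and SD 20, assuming normal changes and a placebo mean of 0, the responder endpoint has 39% to 54% power with 30 and 15 subjects, and at that sample size reaches 80% at a difference of about 26 to 28 points, depending on the test.

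This costs one sentence in two places and needs no new data. It does not raise the power; it corrects how a non-significant result would be read.

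Separately, check whether the SAP names a sparse-data method for the responder endpoint. If it does, cite it. If not, a penalised or exact odds ratio and a risk difference with a score interval can be reported beside the stated logistic analysis. These should be labelled as added after unblinding, since Part 1 was unblinded on 02-Mar-2020 and this version is dated 08-Oct-2020. The choice among such methods is open, and with an empty cell a penalised odds ratio will have a very wide upper limit.

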10.4.4 Safety Analysis

The safety objectives of this study are to evaluate the safety and tolerability profile of inclisiran.

10.4.4.1 Adverse Events

The Medical Dictionary for Regulatory Activities (MedDRA) dictionary will be used for coding AEs. An AE (classified by preferred term) occurring during the investigational product treatment period will be counted as a treatment emergent AE (TEAE) either if it is not present at baseline or if it is present at baseline but increased in severity during the treatment period.

The number (percentage) of subjects reporting TEAEs for each preferred term will be tabulated by system-organ class, by system-organ class and severity, and by system-organ class and relationship to investigational product. If more than one event occurred with the same preferred term for the same subject, the subject will be counted only once for that preferred term using the most severe or related occurrence for the summary by severity, or relationship to investigational product, respectively.

10.4.4.2 Laboratory Tests

Laboratory values will be summarized by treatment group, including changes and percent changes from baseline at each time point. Analyses will also be performed for each laboratory parameter by treatment group for incidence rates of potentially clinical significant (PCS) values for subjects without PCS value at baseline.

Numerical values of laboratory parameters from different local laboratories with different units and normal ranges will be converted to the conventional units and normalized to a standard set of reference/normal ranges. The normalization process will be performed and separated by each of the laboratory parameters. A shift analysis by normal range will be done which counts the number of patients with a low, normal or high value at baseline and a low, normal or high value post baseline.

10.4.4.3 Vital Signs

Change and percent change from baseline in vital signs will be summarized descriptively at each scheduled time point by treatment group.

10.4.4.4 Neurological Examinations

The percentage of subjects with a treatment-emergent abnormal neurological examination and the specific abnormality reported will be summarized by treatment group.

10.4.4.5 Pharmacodynamic Parameters

Pharmacodynamic biomarker samples will be collected and stored for up to 1 year following the completion of the last subject for research purposes to identify and/or verify biomarkers that are predictive of response to inclisiran treatment (in terms of efficacy, safety and tolerability).

10.5 Interim Analysis

No formal interim analysis will be performed in this study.

10.5.1 Interim Safety Review

The Independent Data Monitoring Committee (IDMC) will review safety data 90 days after the first 20 subjects receive the first injection of inclisiran or placebo. Thereafter the IDMC will review safety data every 3 months until all patients have reached Day 180 unless requested otherwise by the IDMC. A recommendation will be made to continue, stop or amend the study at any of these reviews. Following Day 180 the unblinded data will be reviewed by the IDMC.

11 Records Retention

The US FDA regulations require all investigators participating in clinical study drug studies to maintain detailed clinical data for one of the following periods:

- At least two years following the date on which a New Drug Application is approved by the FDA, or
- Two years after the Sponsor notifies the investigator that no further application is to be filed with the FDA.

Similarly, current EU Directives / Regulations and International Conference on Harmonisation (ICH) guidelines collectively require that essential clinical study documents (including case report forms) other than patient's medical files must be retained for the following time period:

- for at least 15 years after completion or discontinuation of the study,
- or for at least two years after the granting of the last marketing authorization in the European Community and when there are no pending or contemplated marketing applications in the European Community,
- or for at least two years after formal discontinuation of clinical development of the investigational product.

Subject's medical files should be retained in accordance with applicable legislation and in accordance with the maximum period of time permitted by the hospital, institution or private practice. The documents can be retained for a longer period, however, if required by the applicable regulatory requirements or by agreement with the sponsor.

To comply with these requirements, the investigator will not dispose of any records relevant to this study without either (1) written permission from the Sponsor or (2) providing an opportunity for the Sponsor to collect such records. The investigator shall take responsibility for maintaining adequate and accurate hard copy source documents of all observations and data generated during this study, including the hard copy or discs received from the sponsor of the final data. Such documentation is subject to inspection by the Sponsor or its agents, the FDA and/or other regulatory agencies.

12 Quality Control and Quality Assurance

12.1 Monitoring

The Sponsor has ethical, legal and scientific obligations to carefully follow this study in accordance with established research principles and applicable regulations. The investigator, as part of his responsibilities, is expected to cooperate with the Sponsor in ensuring that the study adheres to the protocol and GCP requirements.

As part of a concerted effort to fulfill these obligations, the Sponsor's monitor will visit the center(s) during the study in accordance with the Monitoring Plan set forth for this study. The investigator will permit the Sponsor to monitor the study as frequently as is deemed necessary and provide access to medical records/source documents to ensure that data are being recorded adequately, that data are verifiable and that protocol adherence is satisfactory.

